### 16.2 Classification of AEs

#### 16.2.1 AE severity

Each AE will be categorized in terms of their severity as defined in table below.

Severity	Definition
Mild	Events, signs or symptoms that are easily tolerated by the subject, or are clinical or diagnostic observations of the investigator
Moderate	Events, signs or symptoms that cause discomfort and interfere with normal functioning. Local or noninvasive intervention may be indicated
Severe	Events, signs or symptoms that disable the subject, are medically significant, lead to hospitalization or prolongation of hospitalization

### 16.2.2 AE causality

The relationship of each AE to the study drug (i.e., mometasone furoate), study devices (i.e., PROPEL® Contour Sinus Implant, VenSure™ Nav Balloon Device, Cube Navigation System), and procedures (i.e., frontal BSD, implant placement) will be evaluated by PIs and categorized as defined in table below.

Strength of Relationship	Definition
Definitely	Clear-cut temporal association, and no other possible cause
Probably	Clear-cut temporal association, and a potential alternative etiology are not apparent
Unlikely	Does not follow a reasonable temporal association; or causal relationship with the drug, devices or procedures involved in the research is unlikely but cannot be completely ruled out
Not-related	AE is completely independent of study product administration; and/or evidence exists that the event is definitely related to another etiology
Indeterminate	Information gathered about the AE is not sufficient to arrive at a definite conclusion about causal relationship

Any AE that is determined by a participating investigator to be related (definitely or probably related) to the study drug, study device, or procedure will be categorized as device related. All AEs will be attributed separately to each device (i.e., PROPEL Contour Sinus Implant, VenSure™ Nav Balloon Device, Cube Navigation System), each study procedure (i.e., inflation device, BSD, implant placement), and any other in-office baseline procedures, as well as those that are a mix or indistinguishable.

For device-related AE (anticipated or unexpected/unanticipated), the sponsor may request source documentation to confirm the relationship of the AE to the study devices and may review such AE with an independent otolaryngologist, as needed.

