Unanticipated adverse device effect (UADE)	Any serious adverse effect on health or safety or any life-threatening problem or death caused by, or associated with, a device, if that effect, problem, or death was not previously identified in nature, severity, or degree of incidence in the investigational plan or application, or any other unanticipated serious problem associated with a device that relates to the rights, safety, or welfare of subjects. [21 CFR 812]  A UADE is comparable to an unexpected serious adverse device effect (USADE) as defined in ISO 14155:2020 (see definition below), although it doesn't include an "S" for serious in the FDA's acronym. NOTE: The occurrence of a diagnostic or elective surgical procedure for a pre-existing condition, unless the condition becomes more severe or increases in frequency because of the device, would not be considered an adverse device effect (ADE).
Unanticipated serious adverse device effect (USADE)	Any serious adverse device effect (SADE) which by its nature, incidence, severity or outcome has not been identified in the current version of the risk analysis report. [ISO 14155:2020; 21 CFR 812]

	
If the nature, incidence, severity or outcome of a SADE has been identified in the device's risk analysis report, it is considered an anticipated SADE (or ASADE).

Use error	
User action or lack of user action while using the medical device that leads to a different result than that intended by the manufacturer or expected by the user.
 
Use error includes the inability of the user to complete a task.
 
Use errors can result from a mismatch between the characteristics of the user, user interface, task or use environment.
 
Users might be aware or unaware that a use error has occurred.
 
An unexpected physiological response of the patient is not by itself considered a use error.
 
A malfunction of a medical device that causes an unexpected result is not considered a use error.
 
[ISO 14155:2020]

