## 16 ASSESSMENT OF SAFETY

### 16.1 Specification of Safety Parameters

Adverse events (AE) for each subject from the time the subject gives written informed consent (enrollment) through Day 180 (end of study) will be recorded in the EDC system and monitored. Each AE will be evaluated by clinical investigators in terms of severity (i.e., mild, moderate, severe) as well as strength of relationship (i.e., not related, unlikely related, probably related, definitely related, indeterminate) to the study drug (mometasone furoate), study devices, and procedures (BSD, implant placement). Each AE will be reviewed by sponsor in accordance with sponsor's SOP. The study sponsor is responsible for ensuring that all AEs are appropriately recorded, adjudicated and, when applicable, reported to the government(s), ethics committee(s) and other study centers per applicable regulations.

Subjects with CRS experience a persisting set of symptoms associated with the disease and may continue to present with a wide range of symptoms during the recovery process after in-office balloon dilation. These may include symptoms such as pain and discomfort, headache, decreased sense of smell, crusting, epistaxis, and other symptoms. Patients healing appropriately after in-office procedure may suffer from acute infections and/or inflammatory exacerbations unrelated to the procedure due to the natural course of their CRS. Therefore, clinical investigators will evaluate the occurrence of AEs excluding usual post-operative recovery signs and symptoms experienced by study subjects, unless corroborated by objective findings and/or requiring specific medical or therapeutic interventions (e.g., antibiotics, repeat ESS).

Note: The need for medical or surgical intervention in the FSO post-dilation that is captured on the endoscopic assessment CRF will not be considered as an AE. Likewise, other endoscopic findings such as inflammation, adhesion/scarring, and edema of the FSO will not be considered as AEs.

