### 16.2.3 AE expectedness

It is sponsor's responsibility to evaluate expectedness of each device-related AE in accordance with sponsor's SOP. Expectedness is categorized as defined in table below.

Expectedness	Definition
Expected	AE is consistent with the risk information described in the ICF, IFU and clinical study protocol (see Section 17)
Unanticipated or Unexpected	AE is considered UADE or USADE if it is not consistent with the risk information described in the ICF, IFU and clinical study protocol (see Section 17).

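### Indeterminate AEs, and AEs with a plausible but unproven alternative cause, fall outside the device-related class by default; Protocol 16.2.3, 16.3 and the UADE definition differ on which events need an expectedness assessment

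*Protocol*

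**What the plan says.** Protocol 16.1 has investigators rate each AE on a five-level scale: "strength of relationship (i.e., not related, unlikely related, probably related, definitely related, indeterminate". Section 16.2.2 defines the levels:

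- *Probably*: "Clear-cut temporal association, and a potential alternative etiology are not apparent".
- *Unlikely*, second limb: "causal relationship with the drug, devices or procedures involved in the research is unlikely but cannot be completely ruled out".
- *Not-related*, second limb: "evidence exists that the event is definitely related to another etiology".
- The remaining level, *Indeterminate*, is for events where the evidence falls short: "Information gathered about the AE is not sufficient to arrive at a definite conclusion about causal relationship".

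The same section then sets the counting rule: "Any AE that is determined by a participating investigator to be related (definitely or probably related" to the study drug, a study device or a procedure is categorized as device related. It gives no default for *Indeterminate*.

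Section 16.2.3 makes it the sponsor's "responsibility to evaluate expectedness of each device-related AE". Section 4 defines a UADE more widely, as a serious effect "caused by, or associated with, a device" and not previously identified.

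Section 16.3 has the sponsor review, for each AE, whether the severity, causality and expectedness classifications are appropriate. It sends a disagreement between sponsor and investigator on seriousness or causality to an independent adjudicator. SAP 9.7 tabulates AEs and serious AEs (SAEs), including adverse device effects (ADEs), UADEs and unanticipated serious adverse device effects (USADEs). It lists every AE with its strength of relationship. It does not say which relationship levels make an event an ADE, or how an indeterminate event is counted.

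**The concern.** In chronic rhinosinusitis a competing explanation is usually at hand. Protocol 16.1 itself says that subjects who are healing normally may have infections or inflammatory flares from the natural course of the disease. Section 17.1 lists infection, epistaxis, headache and facial pain among the balloon risks. For such events the *Probably* level is hard to reach, because it needs the absence of an apparent alternative.

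The design puts weight on this scale. Every treated subject has the implant on one side and none on the other. An event that cannot be assigned to a side therefore has no comparison group, and its attribution rests on the relationship rating. The investigators who give that rating are unblinded (Protocol 19.3). Protocol 9.4 names ADEs, SAEs, UADEs and USADEs as the measures by which safety is determined.

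Two things are at stake: whether the device-related figures show the uncertain events, and whether a serious event of uncertain cause must be checked against the known risks.

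**Working it through.** No figure in the plan bears on this point, so there is none to reproduce. The check sets the sections side by side.

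**1. Which ratings qualify (Protocol 16.2.2).**

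| Rating | Device related? |
|---|---|
| Definitely | Yes |
| Probably | Yes |
| Unlikely | No |
| Not-related | No |
| Indeterminate | No, by default |

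Two of five ratings qualify and three do not.

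**2. Where an uncertain event lands.** Take an event with a clear temporal link and a plausible, unproven alternative cause.

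- *Definitely* fails, because another cause is possible.
- *Probably* fails, because an alternative is apparent.
- *Not-related* fails, because the alternative is not established.
- *Unlikely* fits only if the investigator judges causation improbable; its first limb, no reasonable temporal association, does not apply.
- *Indeterminate* fits only if the difficulty is described as a lack of information.

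No level describes the event well, and both levels left to it are outside the class. An event definitely due to something else is different: it is properly *Not-related*, and nothing is wrong there.

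**3. Which events need an expectedness assessment.**

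| Source | Scope |
|---|---|
| Protocol 16.2.3 | Device-related AEs |
| Protocol 16.3 | Classification reviewed for each AE |
| Protocol 4, UADE | Serious effects caused by or associated with a device |

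The three scopes differ. Section 16.3 asks whether an expectedness classification is appropriate, but 16.2.3 requires such a classification only for device-related AEs.

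**4. Which events enter the device-effect tables (SAP 9.7).** No threshold is given. The ADE definition in Protocol 4 does not refer to the definite/probable rule either. Using that rule is the natural reading, but it is an inference. SAP 9.7 also takes the maximum relationship when an AE recurs in a subject, without saying where *Indeterminate* ranks.

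**5. Size.** The documents give no frequency for indeterminate events. Assume that all 80 randomized subjects are exposed to the implant. Each subject with an indeterminate event and no other device-related event then shifts the device-related incidence by 1/80 = 0.0125, or 1.25 percentage points. With k such subjects, the gap between the two ways of counting is k × 1.25 points. It is zero if there are none, and k cannot be set from the documents.

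**The case against.** A reader might infer that these events drop out of safety reporting, are never assessed for expectedness, and bias the ADE and UADE counts downward. The documents do not support that reading.

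- **Sponsor review.** Protocol 16.3 covers each AE. It includes the need for more information from the site, which speaks directly to an event left indeterminate, and the requirements for reporting to FDA and the IRB. An adjudicated causality is final and used in all analyses, so the investigator's rating can be overturned.
- **Notification.** Protocol 16.4 requires a verbal report of every SAE to the sponsor within 24 hours and a written one within 5 working days, whatever the causality.
- **Tables.** All AEs stay in the overall incidence (Protocol 18.5) and in the SAP 9.7 tables and listings, with their relationship. A reader can recount them.
- **Direction.** The 16.2.2 rule also widens the class, because an event related only to a procedure counts as device related. With the ADE threshold unstated as well, no net downward bias is shown.
- **Unseen procedure.** The sponsor's operating procedure, which we do not have, may settle how indeterminate events are handled.
- **Convention.** Relabelling every information-poor event as device related would replace one convention with another. No efficacy criterion depends on it.

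These points stand, and they limit the finding. They do not remove it. Adjudication starts only on disagreement; if sponsor and investigator both accept *Indeterminate*, nothing is triggered. The adjudicator rules on seriousness and causality, not expectedness. The device-related reporting row in 16.4 does not reach non-serious indeterminate events. The scopes in 16.2.3 and 16.3 still differ, and the SAP still has no counting rule.

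**Conclusion.** The point holds as one of classification and clarity. By default, indeterminate events and events with a clear temporal link but a plausible, unproven alternative are outside the device-related class. If the device-effect tables follow that threshold, device-related counts can be understated; by how much is unknown. The sections on expectedness and the UADE definition are not aligned and must be reconciled.

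The conclusion assumes that the protocol text governs where the operating procedure cannot be seen, and that SAP 9.7 applies the 16.2.2 rule. If SAP 9.7 uses another rule, the possible understatement falls away, but the need to state the rule and to reconcile expectedness remains. The change is worth making because the data are already collected and it can alter both the reported safety figures and UADE screening.

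**What to change.** 1. **Protocol 16.2.3.** Align it with 16.3 and the UADE definition by stating that expectedness is evaluated for every SAE not rated *Not-related*. This covers serious events rated *Unlikely* as well as *Indeterminate*.
2. **SAP 9.7.** State that the device-related count uses *definitely* and *probably*. Keep that as the definition, and add a second column that also counts *Indeterminate* events as device related. The same sentence can say where *Indeterminate* ranks when the maximum relationship is taken.

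The second column will not pick up non-serious events that were rated *Unlikely*; those remain visible in the listings.

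The cost is wording in two documents, one extra table column, a few more expectedness reviews, and a second figure that is less favourable to the device. No re-rating or new data collection is needed, because the relationship is already recorded for each AE.

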### 16.2.3 AE expectedness

It is sponsor's responsibility to evaluate expectedness of each device-related AE in accordance with sponsor's SOP. Expectedness is categorized as defined in table below.

Expectedness	Definition
Expected	AE is consistent with the risk information described in the ICF, IFU and clinical study protocol (see Section 17)
Unanticipated or Unexpected	AE is considered UADE or USADE if it is not consistent with the risk information described in the ICF, IFU and clinical study protocol (see Section 17).

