## 17.1 Potential Risks

Risks associated with balloon dilation of the sinuses, as well as the placement and use of the PROPEL Contour Sinus Implant in the FSO are anticipated to be similar to those experienced by subjects who undergo balloon dilation of the sinuses as well as placement of other sinus stents.

Consequently, the risks potentially associated with the use of the sinus balloons may include but are not limited to the following:

- Epistaxis
- Cerebrospinal fluid leak
- Pneumocephalus
- Damage of the orbital wall or other ocular structures
- Impaired or loss of vision
- Impaired tearing
- Periorbital cellulitis/edema
- Infection
- Facial/nasal pain
- Facial/nasal discomfort
- Headache

Accordingly, the risks potentially associated with the placement of the PROPEL Contour Sinus Implant are:

- Special care should be taken to avoid bending, twisting or damaging the implant.
- The implant is not designed to be modified by the physician.
- The implant is not intended to be compressed and loaded into the delivery system more than two times.
- The implant must be placed under endoscopic visualization.
- The implant exhibits no antimicrobial properties.
- Foreign body reaction may occur as is possible with most surgical adjuncts.
- In rare instances, the physiochemical condition associated with sinus surgery, both with and without sinus implants or packing, may present a risk of toxic shock syndrome (TSS).
- Pediatric Use: The safety and effectiveness of the implant in pediatric patients have not been established.

- Pregnancy and Nursing Females: The safety and effectiveness of the implant in pregnant or nursing females have not been established.

Risks or side effects associated with the intranasal use of intranasal mometasone furoate (study drug):

- Nasal irritation
- Hypersensitivity reaction
- Intranasal bleeding
- Localized infection (bacterial, fungal colonization or viral) in the nose or pharynx
- Nasal burning
- Nasal dryness
- Susceptibility to secondary infections due to bacteria, fungi or viruses
- Glaucoma or elevation of intraocular pressure
- Cataracts or change in lens opacities
- Headache
- Pharyngitis

General side effects associated with steroids:

- Alteration of the HPA axis including growth suppression
- Immunosuppression
- Hypersensitivity reactions
- Headache
- Epistaxis
- Coughing
- Vomiting
- Candidiasis
- Glaucoma/elevation in intraocular pressure
- Cataracts or change in lens opacities
- Arthralgia
- Myalgia

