## 19.10 Study Suspension or Early Termination

The study can be discontinued at the discretion of the investigator or study sponsor for reasons including, but not limited to, the following:

- Occurrence of AEs unknown to date in respect to their nature, severity, or duration, or the unexpected incidence of known AEs
- Obtaining new scientific knowledge that shows that the study is no longer valid or necessary
- Insufficient recruitment of subjects
- Unanticipated adverse device effect (UADE) or unanticipated serious adverse device effect (USADE) presenting an unreasonable risk to subjects (sponsor may terminate the study immediately)
- Persistent non-compliance with the protocol
- Persistent non-compliance with applicable ethics committee or regulatory requirements
- Sponsor decision to terminate study

If the study is discontinued or suspended prematurely, the sponsor shall promptly inform all clinical investigator(s)/study center(s) of the termination or suspension and the reason(s) for this. The IRB shall also be informed promptly and provided with the reason(s) for the termination or suspension by the sponsor or by the clinical investigator/investigation center(s). Regulatory authorities and the personal physicians of the subjects may also need to be informed if deemed necessary and provided any blinding information to assist with patient care.

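### Protocol 16.2.3 makes any unexpected device-related AE a UADE or USADE with no seriousness condition, and judges it against different reference documents from Section 4; the two sections need to be reconciled.

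*Protocol*

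**What the plan says.** Protocol Section 16.2.2 sets the pool of events: an AE that an investigator finds definitely or probably related to the study drug, a study device or a procedure "will be categorized as device related".

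Protocol Section 16.2.3 then asks the sponsor to "evaluate expectedness of each device-related AE", and adds: "Expectedness is categorized as defined in table below". The table has two rows. An event that fits the risk information in the consent form, the instructions for use (IFU) and the protocol (with a pointer to Section 17) is expected. For the other row, "AE is considered UADE or USADE if it is not consistent with the risk information described in the ICF, IFU and clinical study protocol".

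Protocol Section 4 defines the same two terms differently.

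- A UADE is a serious effect, a life-threatening problem, a death or another unanticipated serious problem. The effect counts as unanticipated if it "was not previously identified in nature, severity, or degree of incidence in the investigational plan or application".
- A USADE is a serious adverse device effect (SADE) that "by its nature, incidence, severity or outcome has not been identified in the current version of the risk analysis report". A SADE that is in that report is an anticipated one (ASADE).

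Elsewhere, Protocol Section 9.4 refers to Section 4 for these terms, and Section 16.4 lists UADE and USADE among the serious adverse events. SAP 9.7 tabulates UADEs and USADEs by system organ class and preferred term. The SAP expands the abbreviations but does not define the terms, so it inherits whichever protocol rule is applied.

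**The concern.** Section 16.2.3 is the table that the sponsor would use to classify an event, and it departs from the definitions in three respects.

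1. It has no seriousness condition, although it applies to all device-related AEs.
2. It uses the consent form, IFU and protocol as the reference, where Section 4 uses the risk analysis report (USADE, ASADE) or the investigational plan or application (UADE).
3. It replaces Section 4's stated attributes with a general consistency test. It does not say whether all three documents must cover the event or whether one is enough.

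At stake is which events are reported as unanticipated. The label decides entry into the SAP 9.7 UADE/USADE counts. It also decides whether the sponsor's review under Protocol Section 16.3 includes the question of unreasonable risk on recurrence, which is asked only of unanticipated events. The independent adjudicator in 16.3 settles disagreements on seriousness or causality, not on expectedness, so no independent step is stated that would catch a misclassification.

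**Working it through.** The plan gives no figure to reproduce, and no statistical input bears on the point. The check sets the two USADE rules side by side.

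Inputs: a device-related AE with three yes/no attributes.

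- S: serious (Section 4).
- D: covered by the consent form, IFU and protocol (Section 16.2.3), taken as one attribute.
- R: covered by the risk analysis report (Section 4).

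Rules as written:

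- Section 16.2.3: unanticipated (UADE/USADE) if not D.
- Section 4: USADE if S and not R; ASADE if S and R; neither if not S.

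| S | D | R | Under 16.2.3 | Under Section 4 | Agree? |
|---|---|---|---|---|---|
| no | no | no | UADE/USADE | neither | no |
| no | no | yes | UADE/USADE | neither | no |
| no | yes | no | expected | neither | yes |
| no | yes | yes | expected | neither | yes |
| yes | no | no | UADE/USADE | USADE | yes |
| yes | no | yes | UADE/USADE | ASADE | no |
| yes | yes | no | expected | USADE | no |
| yes | yes | yes | expected | ASADE | yes |

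Results:

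- As written, the sections disagree in 4 of 8 cases.
- With S added to 16.2.3 (unanticipated if S and not D), the first two disagreements go and 2 of 8 remain.
- With one shared source but no seriousness condition, D equals R, so four cases are left. One of the four still disagrees: non-serious and not covered.
- With both changes, none disagree.

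So both changes are needed. These are counts of logical cases, not event rates.

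For the UADE the mismatch in reference documents is only partial. Section 4 treats the clinical investigational plan and the clinical study protocol as the same kind of document, so the protocol is a reference under both rules. Section 16.2.3 adds the consent form and IFU and leaves out the application. The seriousness gap applies to the UADE in full.

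Reporting times come from the investigator-to-sponsor table in Protocol Section 16.4. A device-related AE needs notice within 24 hours and a written report within 10 working days. The row for SAE, SADE, UADE and USADE needs notice within 24 hours and a written report within 5 working days. A non-serious event that 16.2.3 makes a UADE falls in both rows, so its written report has two deadlines that differ by 10 − 5 = 5 working days. The 24-hour step is common to both.

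**The case against.** The best defence is that UADE and USADE are defined terms. Section 4 builds seriousness into both, 9.4 refers to Section 4, 16.4 treats both as serious, and the word serious is part of the name USADE. On that reading 16.2.3 supplies only the expectedness axis, beside severity and causality, and nobody would call a trivial event a USADE. That is a sensible reading of intent, and it shows which section is out of line. It does not remove the gap: 16.2.3 covers every device-related AE, offers two rows, and has nowhere to put an event that is unexpected but not serious. The reference documents would also still differ.

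Four stronger readings are tempting, and the documents do not support them.

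- *The rule adds a 24-hour report.* It does not; 16.4 already asks for 24-hour notice of every device-related AE. Serious events keep the 5-day written route as SAE or SADE whatever their expectedness.
- *A serious event of a listed type but of unforeseen severity or frequency would escape the stopping provisions.* Section 19.10 has a separate ground for AEs of unknown nature, severity or duration and for known AEs at an unexpected incidence. Its list is not exhaustive.
- *Section 17 cannot act as a reference for the implant.* Of the nine entries in the 17.1 implant list, two are clinical events (foreign body reaction, toxic shock syndrome); the other seven are cautions or labelling statements, such as "The implant is not designed to be modified by the physician". But 17.1 has 11 + 11 + 12 = 34 further entries for the balloon, intranasal mometasone and steroids in general, and the implant releases mometasone. The consent form and IFU, also part of the reference, are not available here. The seven-of-nine count shows an untidy list, not an unusable one.
- *The UADE/USADE count would move by some stated number.* The documents give no expected event rates, so no such figure can be derived.

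**Conclusion.** The inconsistency is real and rests on the protocol's text alone as far as seriousness is concerned. Taken literally, 16.2.3 turns non-serious unexpected device-related AEs into UADEs or USADEs, against Section 4 and against the use of the terms in 9.4 and 16.4. The consequences are an ambiguous entry rule for the SAP 9.7 UADE/USADE tables, an ambiguous trigger for the unreasonable-risk question in 16.3, and two written-report deadlines for the same event.

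The conflict over reference documents is complete for USADE/ASADE and partial for UADE. A SADE covered by only one of the two sets would be anticipated under one section and unanticipated under the other. Whether any such SADE exists depends on the risk analysis report, the consent form and the IFU, which were not provided. Section 17 presents itself as a summary of a risk/benefit analysis, so the overlap may be large. The sponsor's procedure for rating expectedness was not provided either and may already resolve some of this.

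This is a drafting fault in safety classification. It does not touch the primary endpoint, the key secondary analyses or the sample size.

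**What to change.** 1. In Protocol 16.2.3, reword the second row so that a device-related AE is a UADE/USADE only if it is serious under Section 4 and its nature, severity, incidence or outcome is not identified in one named reference document, with its version.
2. Add a third row for a non-serious event that fails the same test, labelled an unexpected ADE.
3. Use that same document and version for the UADE, USADE and ASADE definitions in Section 4. Section 4 attributes its UADE and USADE texts to 21 CFR 812 and ISO 14155:2020, so the sponsor may prefer to leave those texts intact and add a sentence, repeated in 16.2.3, naming the document that serves as the reference in this study. The choice of document is the sponsor's.
4. In SAP 9.7, state that UADEs and USADEs are counted by this single rule and that unexpected non-serious ADEs are shown separately.
5. Optionally, separate the handling cautions from the clinical risks in the 17.1 implant list.

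The cost is wording in two protocol sections and one SAP section, plus one list if step 5 is taken. No new data, visits or staff are needed. Any events already rated under 16.2.3 should be checked against the reconciled rule before the safety tables are produced.
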